Title: My MS and My Menstrual Cycle

Measuring MS symptoms in relation to menstrual cycles: exploring how MS symptoms may be affected at different times during a menstrual cycle in females living with Multiple Sclerosis

Research Team:

[name], [name], [name], [name], [name], [name], [name], [name], [name], [name], [name].

Objective:

To evaluate the severity and timing of MS symptoms with timing of menstrual cycles in women living with MS.

Methods:

Design:

This project is a prospective observational study of females living with MS, tracking MS symptoms in correlation with time of menstrual cycle, measured and correlated via a smartphone app

Inclusion Criteria:

Participants are required to meet the following criteria:

- Females with diagnosed MS by 2024 McDonald Diagnostic criteria ¹ (biologically sex-based, any gender as long as not on hormonal gender-enhancing therapy)
- ages 16+, still experiencing menstruation with cycles of 23 to 36 days spacing
- have entered menarche, are experiencing menstrual cycles, and have not yet entered menopause
- participants may utilize hormonal contraceptive methods, such as oral contraceptive methods or hormonal IUDs
- English-speaking
- Willing to provide informed consent, mature minors will provide informed consent, their physician will determine whether their level of maturity is appropriate to participate in the study and complete consent as a mature minor
- Have the ability to complete questionnaires and operate the app

Exclusion Criteria:

People will be excluded as per the following criteria:

- diagnosed with CNS inflammation disorders other than MS such as:
 - NMOSD (Neuromyelitis Optica Spectrum Disorder)
 - MOGAD (Myelin Oligodendrocyte Glycoprotein Antibody-associated Disease)
- male or intersex individuals, given the inclusion criteria of requiring a uterus
- females < 15 years of age
- females who have not started menstruation
- females who have stopped menstruation due to menopause or hysterectomy
- pregnant or postpartum women < 1 year after delivery and/or people who currently breastfeeding
- are unable to provide informed consent, or are not deemed a mature minor to complete consent are unable to complete questionnaires and operate the app

Recruitment:

Via treating neurologists (MS clinic or community-based) and/or nurse practitioners; flyers sent through social media newsletters MS Canada and MS research portal via MS Canada and in clinic rooms/waiting rooms neurologists' practices; mass secure patient messaging via connectcare electronic medical records system

Randomization:

n/a

Intervention:

Eligible patients will download the My Normative app, by scanning a link/QR code. Once registered, electronic consent will be collected through the app. Participants will fill out a baseline series of demographics in addition to a series of patient-reported outcome measures (fatigue, patient perceived level of disability, MS patient symptoms screen, sleep, self-efficacy scale, self-perceived cognition and coping levels, motivation for cognition, and depression and anxiety levels) on the app, as well as enter information re: menstrual cycle tracking/hormone levels as prompted by the app. Participants will then track their menstrual cycles for 6 months with completion of patient reported outcome measures: (1) fatigue – MFIS – 5 item;²⁻⁴ (2) depression & anxiety - HADS;⁵ (3) coping (mini-COPC); (4) MFC – motivation for cognition;⁶ (5) MSymptoscreen (screen of common MS symptoms)⁷ and likert scale from 0 to 7 as to self-perceived cognition levels. This will be done five times per month, as per the different phases of the menstrual cycle. At the end of 6 months, participants will complete an exit scale – with all of the above.

Duration of Study Involvement:

6 months (this has been determined to be optimal in capturing 3 months of menstrual cycles)

This study will be a 2 year study with rolling enrollment

Primary outcomes:

Difference in modified MFIS (fatigue) levels, 5 items during menstruation compared to other times of the menstrual cycle ^{3, 4, 8-10}.

Secondary outcomes:

Qualitative self-reported difference:

- **HADS** (Hospital anxiety and depression scale) – 14 items ⁵
- **MNSQ** (Multiple Sclerosis Neuropsychological Screening Questionnaire–Patient Version) - 15 items ¹⁰⁻¹³
- **Two Likert scale** – self perceived cognition levels (0 to 7)
- **Coping** – MS specific – Brief COPE Short Version (Mini-Cope) – 12 items (3 different coping styles: active/adaptive, avoidant/maladaptive, and emotional/neutral ¹⁴)
- **MFC scale** (motivation for cognition)⁶
- **the SymptoMScreen** - 12 item (walking, hand function/dexterity, spasticity & stiffness, bodily pain, sensory symptoms, bladder control, fatigue, vision, dizziness, cognition function, depression, anxiety), (Green et al Applied Neuropsych 2016)

Sample size:

We plan to recruit a convenience sample over 2 years, with a maximum of 300 participants. There are no substantial prior studies to base the sample size calculation upon.

Hypothesis:

Women with MS experience worsening fatigue, as self-reported by MFIS, during menstruation compared to other times during their menstrual cycles.

1.0 Background and Rationale:

MS most commonly occurs in young adults and persists lifelong.^{15, 16} It is associated with a number of physical symptoms such as numbness, weakness, troubles with balance, walking, and vision. However, invisible symptoms of MS are often more debilitating, such as fatigue and cognition (brain fog).¹⁷ MS is more common in women

compared to men, preferentially increasing in women over time as compared to men.¹⁸⁻²¹

There are unique features of multiple sclerosis in women: the course of MS appears to be associated with a number of female-specific features, such as onset in women more after menarche,²² less inflammatory activity of MS during pregnancy, and increase in the first 3 to 6 months postpartum.^{23, 24} Furthermore, exclusive breastfeeding is thought to be slightly neuroprotective in MS.²⁵⁻²⁸ Animal model studies suggested an association between female sex hormones in pregnancy and effects on MS inflammation.²⁹ Therefore, researchers have wondered about the effects of female hormones on the course of MS, with suggested impact upon MRI activity in women living with MS.³⁰⁻³⁴ However, it is controversial as to how and whether female hormones impact MS activity, symptoms of MS, progression of MS.^{35, 36} Two randomized controlled trials of pregnancy-related sex hormones in women with relapsing remitting MS were negative.^{23, 29, 37-39} Despite the lack of definitive association, women with MS have reported fluctuations of MS symptom severity over their menstrual cycles.^{40, 41}

A recent prospective study examining MS symptom severity variability at points throughout women's menstrual cycle was published in 2023; participants reported a number of symptoms at different points during their menstrual cycles and there was a suggestion of less fatigue as measured by the MFIS during the perimenstrual period as compared to the luteal period, not felt to be clinically significant, as well as less variability in fatigue reported by women on continuous hormonal oral contraception compared to those who weren't. The authors conclude that more studies are needed to examine the possible relationship between menstruation and MS symptoms.⁴²

The My Normative platform app has been used in other populations to track menstrual cycles in relation to various symptoms for women in the general population and other conditions.(mynormative.ca) We hope to examine MS-related symptoms to stages of the menstrual cycle, as measured by the My Normative platform.(mynormative.ca) We hypothesize that MS-related fatigue would be greater in the luteal phase of the cycle as compared to other times of women's menstrual cycles, as measured by the MFIS-5 item.³ Secondary outcomes will include impact of menstrual cycle stage upon cognition as measured by the likert scale of self-perceived cognitive levels from 1 to 7, various MS symptoms as measured by the SymptoMScreen (walking, hand function/dexterity, spasticity & stiffness, bodily pain, sensory symptoms, bladder control, fatigue, vision, dizziness, cognition function, depression, anxiety),⁷ MFC scale (motivation for cognition)⁶ and coping (the mini-cope)¹⁴ over a 6 month period with a minimum of 3 months of menstrual cycle tracking. The My Normative platform tracks menstrual cycles in five phases: (1) menstrual phase; (2) follicular phase; (3) ovulation phase; (4) Luteal phase early; (5) luteal phase late

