2.0 Proposed Research

Hypothesis:

Women with MS experience worsening of fatigue, as self-reported by MFIS, during menstruation compared to other times during their menstrual cycles.

Design:

Prospective observational self-enrolled study on mobile app.

Setting:

online, app reporting

Subjects:

Females living with MS, who experience menstruation.

Inclusion Criteria:

Participants are required to meet the following criteria:

- Females with diagnosed MS by 2017 McDonald criteria ¹ (biologically sex-based, any gender as long as not on hormonal gender-enhancing therapy)
- ages 16+, still experiencing menstruation with cycles of 23 to 36 days spacing
- have entered menarche, are experiencing menstrual cycles, and have not yet entered menopause
- participants may utilize hormonal contraceptive methods, such as oral contraceptive methods or hormonal IUDs
- English-speaking
- Willing to provide informed consent, mature minors will provide informed consent, their physician will determine whether their level of maturity is appropriate to participate in the study and complete consent as a mature minor
- Have the ability to complete questionnaires and operate the app

Exclusion Criteria:

People will be excluded as per the following criteria:

- diagnosed with other CNS inflammation disorders than MS
- male or intersex individuals, given the inclusion criteria of requiring a uterus
- females < 15 years of age
- females who have not started menstruation
- females who have stopped menstruation due to menopause or hysterectomy

- pregnant or postpartum women x 1 year after delivery and/or people who currently breastfeeding
- are unable to provide informed consent
- are unable to complete questionnaires and operate the app

Randomization:

n/a

Questionnaires:

Baseline:

- **PDDS** – single scale (physical disability measure) Patient Determined Disease Steps ⁴³
- **Full MFIS** – Modified Fatigue Impact Scale (21 point scale) – fatigue ^{2, 8, 9}
- **HADS** (anxiety & depression) – Hospital Anxiety & Depression Scale (14 items)⁵
- **PHQ9** – Patient Health Questionnaire (depression & anxiety) (9 items)^{44, 45}
- **MSNQ** (cognition) (15 item)¹¹⁻¹³
- **Mini Cope** (coping) (12 item)⁴⁶
- **Pittsburgh sleep quality index** (sleep quality) (24 items)⁴⁷
- **the SymptoMScreen** (12 item) (walking, hand function/dexterity, spasticity & stiffness, bodily pain, sensory symptoms, bladder control, fatigue, vision, dizziness, cognition function, depression, anxiety)^{7, 42}

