Taylor et al completed a pilot study, published in 2023, on menstrual cycle and fatigue symptoms in eumenorrheic women living with MS. There was a suggestion of less fatigue in the perimenstrual period compared to the luteal portion of the cycle, and less fluctuation in symptom severity over the cycle for women on continuous hormonal oral contraception. There was a lot of difficulty recruiting for this study with over 200 women contacted and 70 enrolled and 47 providing more than 4 weeks of data for a 6 month period.⁴² Despite the challenges faced by these authors, and anticipating a 20% dropout, we plan to try to recruit a maximum of 300 participants over 2 years. There are no substantial prior studies to base the sample size calculation upon.

Analytical Plan:

We will calculate summary statistics for primary and secondary outcomes across different menstrual cycle phases. We will conduct hypothesis tests (e.g., t-tests, ANOVA) to determine if there are statistically significant crude differences in MS symptom severity or relapse rates among different menstrual cycle phases and explore the relationship between the timing of the menstrual cycle and MS symptom severity using correlation coefficients (e.g., Pearson's correlation). We will perform regression analysis to identify any potential predictors of MS symptom severity, including menstrual cycle phase, age, duration of MS, and other relevant covariates and stratify the analysis by age groups to explore for effect modification by reproductive stage of youth, early adulthood (reproductive years) and later adulthood (peri-menopause), respectively defined as participants < 20 years old, 20 to 40 years old, > 40 years old. We will control for potential confounding variables, such as medication use, comorbidities, and lifestyle factors, in these adjusted models. Finally, we will perform sensitivity analysis to assess the robustness of the results by varying assumptions or analytical methods. Finally, we will provide descriptive measures of baseline characteristics/demographics.

Feasibility:

This study will be carried out through the reciprocal ethics process at the Universities of Alberta and Calgary. Each MS Clinic at each clinic follows about 5000 PwMS in Alberta. MS affects 3 women to every man, with average onset between ages 20 to 40. Therefore, both clinics see many women with MS who are at ages who experience menarche.

Timelines:

2 years, each site to recruit 150 participants maximum

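### Section 1.0 predicts that fatigue peaks in the luteal phase, the primary outcome and both Hypothesis sections point to menstruation, and the Analytical Plan names no primary contrast

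*Combined protocol and SAP*

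**What the plan says.** Four places in the protocol state what is expected of fatigue over the cycle.

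- Methods, Primary outcomes: "Difference in modified MFIS (fatigue) levels, 5 items during menstruation compared to other times of the menstrual cycle". No direction is given.
- Synopsis, Hypothesis: "Women with MS experience worsening fatigue, as self-reported by MFIS, during menstruation compared to other times during their menstrual cycles".
- Section 2.0, Hypothesis: "Women with MS experience worsening of fatigue, as self-reported by MFIS, during menstruation compared to other times during their menstrual cycles".
- Section 1.0, Background and Rationale: "We hypothesize that MS-related fatigue would be greater in the luteal phase of the cycle as compared to other times". The sentence goes on to name the 5-item MFIS, and the next one begins "Secondary outcomes will include impact of menstrual cycle stage upon cognition".

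Section 1.0 lists the phases the app tracks: "1) menstrual phase; (2) follicular phase; (3) ovulation phase; (4) Luteal phase early; (5) luteal phase late". On frequency, the Intervention section says "This will be done five times per month, as per the different phases of the menstrual cycle", which I read as one assessment per phase.

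The Analytical Plan opens with "We will calculate summary statistics for primary and secondary outcomes across different menstrual cycle phases". It then lists t-tests and ANOVA, as examples, for differences among phases, followed by correlation and regression. It gives no primary contrast, reference phase, direction or alpha.

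**The concern.** The luteal statement is the investigators' own prediction, on the primary instrument, placed just before the secondary outcomes are introduced. That is where a primary hypothesis would normally stand. It also agrees in direction with the pilot study the protocol cites, which suggested less fatigue around menstruation than in the luteal phase. It therefore cannot simply be dismissed as a slip.

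The five phases keep menstruation apart from early and late luteal, so each hypothesis puts the other's peak into its own comparator. The Analytical Plan could settle which comparison is primary, but it does not. At stake is how the only primary endpoint is read: a menstrual excess or a luteal excess could each be presented as the predicted result, with a sentence of the protocol to cite.

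**Working it through.** There is no figure in the plan to reproduce. The sample of 300 is a convenience maximum, and alpha, power, effect size and standard deviation are not stated. The check is a comparison of text, plus arithmetic on what each statement would estimate.

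**Inputs.** The five phases come from section 1.0. Equal weight per phase is my assumption; it fits one assessment per phase. Two-sided alpha 0.05 is also assumed.

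**Contrasts**, in the order menstrual, follicular, ovulation, early luteal, late luteal:

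- Menstruation against the rest: A = (1, -1/4, -1/4, -1/4, -1/4)
- Luteal against the rest: B = (-1/3, -1/3, -1/3, 1/2, 1/2)

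**Step 1. What each contrast shows when the other hypothesis is true.**

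- Rise of D in both luteal phases only: A = 0 - (D + D)/4 = -0.5D, while B = +D.
- Rise of D in menstruation only: B = 0 - D/3 = -0.33D, while A = +D.

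**Step 2. When both hold.** Let the luteal rise be 1, the menstrual rise m, and the other phases flat.

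- A = m - (1 + 1)/4 = m - 0.5, positive when m > 0.5.
- B = 1 - m/3, positive when m < 3.
- Both are positive for 0.5 < m < 3.

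**Step 3. Error rate if either excess may be claimed.** Assume independent phase errors of equal variance (equal correlation between phases gives the same answer).

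- A·B = -1/3 + 2(1/12) - 2(1/8) = -0.417
- A·A = 1 + 4/16 = 1.25; B·B = 3/9 + 2/4 = 0.833
- Correlation = -0.417 / √(1.25 × 0.833) = -0.408
- One contrast in its predicted direction: P(Z > 1.96) = 0.025
- Either contrast in its predicted direction: 0.025 + 0.025 - P(both) = 0.0500, since P(both) is negligible at this negative correlation

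The result stays at 0.0500 when first-order autoregressive correlations between phases of 0.3 to 0.9 are used instead.

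**Step 4. Cost of making both confirmatory.** At 0.025 each, the critical value is 2.241.

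- A contrast with 80% power at 0.05 has non-centrality 1.960 + 0.842 = 2.802.
- Its power becomes P(Z > 2.241 - 2.802) = 0.712.
- Keeping 80% would need ((2.241 + 0.842)/2.802)² = 1.21 times as many women.

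**The case against.** The strongest reply is that the protocol already answers the question. It has one section headed Primary outcomes, which names one contrast, and both sections headed Hypothesis agree with it. The outlier is a single sentence in the background, next to the pilot result it echoes. The Analytical Plan refers to primary outcomes, and those are defined elsewhere. The study is observational, with a convenience sample. Much of this stands: it makes menstruation the likelier intent and lowers the severity. It does not remove the conflict, because the background sentence is a stated hypothesis on the primary measure and the plan commits to significance tests without carrying the labelled contrast forward.

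Three stronger readings are tempting, and the documents do not support them.

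- A reader might infer that the plan has no primary outcome. It has one; what is missing is its contrast in the Analytical Plan.
- A reader might infer that the hypotheses exclude each other. Step 2 shows that they do not. The phase list in section 2.0 puts late luteal directly before the next period, so a rise spanning both could satisfy both statements. The primary outcome itself gives no direction.
- A reader might count significance in either direction on either contrast, which gives 9.3% instead of 5.0%. That includes results opposite to each prediction, which nobody could report as the hypothesised excess. The directional figures are the ones that match the harm.

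**Conclusion.** The inconsistency is real, lies in current text and concerns the only primary endpoint. It should be fixed before data are seen. It is not a fatal flaw, because all three labelled statements agree.

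The two wordings estimate different quantities, and a pattern that fully supports one can count against the other (-0.5D or -0.33D). If both remained open, the directional false-claim rate would be about 5.0% instead of 2.5%. That is an illustration: it rests on an assumed two-sided 0.05, equal phase weights and the correlation structures tried. The contradiction itself needs none of these assumptions.

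**What to change.** 1. Before data are seen, make the Primary outcomes section, both Hypothesis sections and section 1.0 agree on one primary hypothesis. The choice is the investigators'. The smallest change is to relabel the luteal sentence in section 1.0 as a named secondary contrast. If luteal is the main hypothesis, the other three places change instead.

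2. State the primary contrast in the Analytical Plan. If menstruation is kept, an example is: menstrual-phase MFIS-5 minus the equally weighted mean of the other four phases, two-sided alpha 0.05, with a 95% confidence interval. Weighting by time in each phase is also possible; the plan should say which is used.

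3. Estimate it within woman. Either average each woman's contrast over her cycles, or fit a mixed model that lets the phase effect vary between women. A random intercept alone is not enough. Women contribute several cycles, and the pilot cited in the protocol suggests that fluctuation differs between women (less on continuous hormonal contraception). The interval for the phase contrast would then be too narrow.

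4. Report the other contrast and all five phase means as secondary, with confidence intervals.

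5. If both contrasts are to be confirmatory, test each at 0.025. Power of 80% then falls to about 71%, or about 21% more women are needed to keep it.

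The cost is wording, with no new data or visits. The downside of keeping menstruation as the single primary is that a luteal excess can no longer be presented as the primary result.

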2.0 Proposed Research

Hypothesis:

Women with MS experience worsening of fatigue, as self-reported by MFIS, during menstruation compared to other times during their menstrual cycles.

Design:

Prospective observational self-enrolled study on mobile app.

Setting:

online, app reporting

Subjects:

Females living with MS, who experience menstruation.

Inclusion Criteria:

Participants are required to meet the following criteria:

- Females with diagnosed MS by 2017 McDonald criteria ¹ (biologically sex-based, any gender as long as not on hormonal gender-enhancing therapy)
- ages 16+, still experiencing menstruation with cycles of 23 to 36 days spacing
- have entered menarche, are experiencing menstrual cycles, and have not yet entered menopause
- participants may utilize hormonal contraceptive methods, such as oral contraceptive methods or hormonal IUDs
- English-speaking
- Willing to provide informed consent, mature minors will provide informed consent, their physician will determine whether their level of maturity is appropriate to participate in the study and complete consent as a mature minor
- Have the ability to complete questionnaires and operate the app

Exclusion Criteria:

People will be excluded as per the following criteria:

- diagnosed with other CNS inflammation disorders than MS
- male or intersex individuals, given the inclusion criteria of requiring a uterus
- females < 15 years of age
- females who have not started menstruation
- females who have stopped menstruation due to menopause or hysterectomy

- pregnant or postpartum women x 1 year after delivery and/or people who currently breastfeeding
- are unable to provide informed consent
- are unable to complete questionnaires and operate the app

Randomization:

n/a

Questionnaires:

Baseline:

- **PDDS** – single scale (physical disability measure) Patient Determined Disease Steps ⁴³
- **Full MFIS** – Modified Fatigue Impact Scale (21 point scale) – fatigue ^{2, 8, 9}
- **HADS** (anxiety & depression) – Hospital Anxiety & Depression Scale (14 items)⁵
- **PHQ9** – Patient Health Questionnaire (depression & anxiety) (9 items)^{44, 45}
- **MSNQ** (cognition) (15 item)¹¹⁻¹³
- **Mini Cope** (coping) (12 item)⁴⁶
- **Pittsburgh sleep quality index** (sleep quality) (24 items)⁴⁷
- **the SymptoMScreen** (12 item) (walking, hand function/dexterity, spasticity & stiffness, bodily pain, sensory symptoms, bladder control, fatigue, vision, dizziness, cognition function, depression, anxiety)^{7, 42}
- **MFC scale** (Motivation for Cognition) (10 item)⁶
- **General factors**
 - Demographics (age, race, ethnicity, marital status, level of education, # children, working outside/inside home), BMI, smoking status
 - Years since onset MS (first symptoms) and diagnosis
 - Disease modifying therapies list
 - Medications listt
- **Menstrual cycle information**
 - Length of cycle
- **Type of contraception**
 - Rhythm method
 - No contraception
 - Barrier
 - Condoms
 - Diaphragm
 - IUD (with hormone, without hormone)

- OCP – type – continuous/not continuous
- **5 time points during the menstrual cycle**
 - 1) Follicular phase, during active menstruation
 - 2) Follicular phase, no menstruation (leading up to ovulation)
 - 3) ovulation phase
 - 4) Luteal phase, first half
 - 5) Luteal phase, second half (this is the 5-7 days before the next period starts)

Each time point:

- MFIS brief 5 item ³
- Cognition Likert scale – self perceived cognition levels (0-7)
- SymptoMSScreen 12 item ⁷
- Mini-COPE (12 item)¹⁴
- MFC scale (motivation for cognition) 10 item⁶
- Longer MFIS point scale once per cycle, alternating timing of long scale done at each time point (3 points within cycle) over study duration (6 months) ^{2, 8, 9}

Study Completion:

- **PDDS** – single scale (physical disability measure) Patient Determined Disease Steps⁴³
- **Full MFIS** – modified fatigue Impact Scale (21 point scale) – fatigue^{2, 8, 9}
- **HADS** (anxiety & depression) – Hospital Anxiety & Depression Scale – 14 items ⁵
- **PHQ9** – patient health questionnaire (depression & anxiety) – 9 items ^{44, 45}
- **MSNQ** (cognition) 15 item ¹¹⁻¹³
- **Cognition Likert scale** – self-perceived cognition levels (0 – 7)
- **Mini Cope** (coping) (12 item) ⁴⁶
- **Pittsburgh sleep quality index** (sleep quality) 24 items ⁴⁷
- **the SymptoMSScreen** - 12 item (walking, hand function/dexterity, spasticity & stiffness, bodily pain, sensory symptoms, bladder control, fatigue, vision, dizziness, cognition function, depression, anxiety) ⁷
- **MFC scale** (motivation for cognition) – 10 item ⁶
- Relapses in past 6 months/use of steroids
- Optional - agreement to be contacted to participate in qualitative interview re: use of app

Sample size:

There is not much information or data to calculate sample size. We plan to recruit 300 women living with MS for this study as a convenience/availability sample from the two

MS Clinics at the University of Alberta and University of Calgary (approximately 150 per site).

Taylor et al completed a pilot study, published in 2023, on menstrual cycle and fatigue symptoms in eumenorrheic women living with MS. There was a suggestion of less fatigue in the perimenstrual period compared to the luteal portion of the cycle, and less fluctuation in symptom severity over the cycle for women on continuous hormonal oral contraception. There was a lot of difficulty recruiting for this study with over 200 women contacted and 70 enrolled and 47 providing more than 4 weeks of data for a 6 month period.⁴² Despite the challenges faced by these authors, and anticipating a 20% dropout, we plan to try to recruit a maximum of 300 participants over 2 years. There are no substantial prior studies to base the sample size calculation upon.

Analytical Plan:

We will calculate summary statistics for primary and secondary outcomes across different menstrual cycle phases. We will conduct hypothesis tests (e.g., t-tests, ANOVA) to determine if there are statistically significant crude differences in MS symptom severity or relapse rates among different menstrual cycle phases and explore the relationship between the timing of the menstrual cycle and MS symptom severity using correlation coefficients (e.g., Pearson's correlation). We will perform regression analysis to identify any potential predictors of MS symptom severity, including menstrual cycle phase, age, duration of MS, and other relevant covariates and stratify the analysis by age groups to explore for effect modification by reproductive stage of youth, early adulthood (reproductive years) and later adulthood (peri-menopause), respectively defined as participants < 20 years old, 20 to 40 years old, > 40 years old. We will control for potential confounding variables, such as medication use, comorbidities, and lifestyle factors, in these adjusted models. Finally, we will perform sensitivity analysis to assess the robustness of the results by varying assumptions or analytical methods. Finally, we will provide descriptive measures of baseline characteristics/demographics.

Feasibility:

This study will be carried out through the reciprocal ethics process at the Universities of Alberta and Calgary. Each MS Clinic at each clinic follows about 5000 PwMS in Alberta. MS affects 3 women to every man, with average onset between ages 20 to 40. Therefore, both clinics see many women with MS who are at ages who experience menarche.

Timelines:

2 years, each site to recruit 150 participants maximum

What this study adds:

Despite the longstanding knowledge of MS risk, onset, and inflammatory activity being related to different hormonal periods throughout women's lives, there is still much that is unknown about the interactions and relationship of female hormones and different

female hormonal states upon MS. In addition, women with MS often report MS symptoms as fluctuating in severity at different points throughout their menstrual cycles. However, despite reporting, literature has not shown definitive correlations between MS symptom severity in relation to different points in the menstrual cycle. If we are able to establish correlations between common MS symptoms at particular points in the menstrual cycle, this will aid researchers, clinicians, and women living with MS around examining different strategies to try to treat MS symptom severity at different points throughout the menstrual cycle. This could include strategies such as that seen with perimenstrual migraine, where women enact prophylactic strategies around the time of menstruation to minimize their migraine headaches during that time of the cycle.⁴⁸

Methodologic Issues:

Patients will self-enroll in the study, through accessing and downloading the app as per instruction. Participants download the My Normative App and become a registered user. Once registered, they will read the consent and then sign consent if they wish to participate in the study. Participants will have the option of withdrawing from the study at any time by simply not responding to cues from the app to fill out their questionnaires. Participants are provided with contact information for the study team, and can withdraw from the study by contacting the study team.

References:

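### Contraception, DMT, other medicines and pregnancy are not asked about again after entry, so ratings after conception or a cycle-suppressing method cannot be recognised as such

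*Combined protocol and SAP*

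**What the plan says.** Under Methods, Intervention: "Participants will then track their menstrual cycles for 6 months", with the symptom scales completed at each phase: "This will be done five times per month, as per the different phases of the menstrual cycle". Eligible women are "ages 16+, still experiencing menstruation with cycles of 23 to 36 days spacing", and "participants may utilize hormonal contraceptive methods, such as oral contraceptive methods or hormonal IUDs". No criterion asks that the method be stable.

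In section 2.0, Questionnaires, the Baseline list takes DMTs, other medicines and type of contraception, including "OCP – type – continuous/not continuous". The Each time point list holds only the short MFIS, the cognition Likert scale, SymptoMScreen, Mini-COPE, the MFC scale and a rotating long MFIS. The Study Completion list repeats the scales, and its only treatment item is "Relapses in past 6 months/use of steroids".

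Pregnancy appears among the exclusions ("pregnant or postpartum women < 1 year after delivery" in the Methods, with similar wording in section 2.0). There is no in-study pregnancy item and no rule for ratings made after conception. The Analytical Plan says: "We will control for potential confounding variables, such as medication use, comorbidities, and lifestyle factors, in these adjusted models". It does not say whether these variables are updated over follow-up, and it does not name contraception as a covariate or stratifier.

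**The concern.** The primary outcome compares fatigue during menstruation with fatigue at other points of the cycle. That comparison needs a cycle with real phases. Two events after entry can remove it: conception, and starting a hormonal method that suppresses the cycle. From then on the woman has no menstruation ratings. If she keeps answering prompts, her ratings can fall only on the non-menstrual side or in a phase that the app predicts but that does not occur. Any change in her fatigue then loads on one side of the contrast, in an unknown direction.

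The plan's own background gives reasons to care. It cites a pilot study suggesting less symptom fluctuation on continuous oral contraception, and it describes lower MS inflammatory activity in pregnancy.

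A second, weaker consequence concerns DMTs and other medicines. The promised adjustment for medication use would apply the entry value to all later cycles. This affects the adjusted and predictor regressions.

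**Working it through.** **What is asked, and when (section 2.0, Questionnaires)**

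| Item | Baseline | Each time point | Study Completion |
|---|---|---|---|
| Contraceptive method | yes | no | no |
| DMT list | yes | no | no |
| Medication list | yes | no | steroids only, no date stated |
| Pregnancy | entry exclusion only | no | no |

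**Length of exposure.** Six months is 365.25/2 = 182.6 days. At the permitted cycle lengths this is 182.6/36 = 5.1 to 182.6/23 = 7.9 cycles. A change midway leaves half of these, about 2.5 to 4 cycles per woman, under an old status. Five ratings a month for six months is nominally 5 × 6 = 30 ratings per woman.

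**Number of women.** The planned maximum is 300 (2 sites × 150). It rests on no power calculation, so there is no derivation to reproduce. With the stated 20% dropout, 300 × 0.8 = 240 complete, giving 240 × 30 = 7,200 nominal ratings.

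**Share of ratings with an out-of-date status.** The documents give no rate of change, so it is assumed. If a share c of women change any status once, at a time uniform over follow-up, the expected share of ratings after the change is c/2:

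| Assumed c | Women among 240 | Share of ratings (c/2) | Ratings of 7,200 |
|---|---|---|---|
| 2% | 4.8 | 1% | 72 |
| 5% | 12 | 2.5% | 180 |
| 10% | 24 | 5% | 360 |
| 20% | 48 | 10% | 720 |

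**Share with a meaningless phase label.** Here c counts every change: DMT, any medicine, any contraceptive method, conception. Only conception and the start of a cycle-suppressing method remove the phases. If these form a fraction f of all changes, with the same timing, the affected share is f × c/2. This is below c/2 whenever f is below 1. The documents give no basis for f, so c/2 is only a ceiling.

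**Which analyses are touched.** After a DMT or medicine change, a cycling woman still rates every phase, so an old covariate value does not systematically favour either side of the menstruation contrast. After conception or cycle suppression she no longer contributes to the menstrual side.

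**The case against.** The strongest reply is that the harm is narrow, and most of it stands.

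- A reader might infer that all ratings under an old status weaken the primary contrast, by up to 10%. The documents do not support this. A DMT change, or a move between non-hormonal methods, leaves the phases intact, and stopping a hormonal method would tend to make the label more meaningful.
- A reader might infer that the primary comparison is analysed under the wrong hormonal status. Contraception is not a named covariate or stratifier, and the crude phase comparison uses no recorded status.
- A reader might infer that women who change treatment become ineligible. Hormonal contraception is allowed and there is no DMT criterion. Pregnancy conflicts directly with eligibility; a method change does so only if it stops menstruation or takes cycles outside 23-36 days.
- A reader might infer that the affected cycles leave no trace. Menstruation is tracked in the app, so a missed period may be visible. However, a gap does not separate pregnancy, continuous contraception, perimenopause and a failure to log, and no rule uses it.

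Two phrases under Methods, Intervention might seem to close the gap: cycle and hormone information is entered when the app prompts, and the exit scale is said to include everything listed before it. The first is in the sentence on baseline entry and gives neither content nor frequency. The second follows a list of outcome measures, and the itemised exit list omits these items; a single exit record without dates could not place a change in a cycle anyway. The app's logging fields are not in the documents, so it may collect more than is described.

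**Conclusion.** The gap is real, and its main consequence is narrow. Following the plan as written, ratings made after conception or cycle suppression can enter only one side of the primary contrast or a predicted phase that does not exist. Their cause cannot reliably be recovered later. For DMTs and other medicines the consequence is out-of-date covariate values in the adjusted and predictor regressions, with no clear bias in the within-woman menstruation contrast.

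At an assumed 2-20% of women changing any status once, on average at mid-follow-up, about 1-10% of ratings carry an out-of-date status. The share with a meaningless phase label is smaller and cannot be put in figures from the documents. The overall effect is probably modest and is concentrated in the women who change. The point is worth acting on because the remedy is cheap and must be in place during data collection.

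**What to change.** 1. Add one yes/no item to the app in each cycle, at the menstruation prompt, with a fallback if no period is logged within 36 days (the upper cycle length for eligibility). It should ask whether the participant has started, stopped or changed contraception, DMT or another regular medicine, or become pregnant, and record the date.
2. Repeat the contraception and medication lists at Study Completion.
3. State in the Analytical Plan that these are time-updated covariates, assigned per cycle.
4. In the primary contrast, use only complete cycles before a reported pregnancy or the start of a cycle-suppressing method. Menstruation ratings and the other-phase ratings of the same cycle are then dropped together. Cutting at the last recorded period would not do, because it keeps a menstruation rating without its matching phases.

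Cost: one short screen per cycle, two lists repeated at exit and a sentence or two in the Analytical Plan. Participants carry a slight extra burden, against 5 + 12 + 12 + 10 = 39 scale items plus the cognition rating already asked at each time point. A small number of ratings is lost from the primary contrast.
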